The time (in days) from randomization to the event plus 1 day will be used for analysis. If death occurred, date is reported in the dedicated eCRF sections “Death – (Endpoint to be adjudicated)” or “Death – (NOT to be adjudicated)”. Subjects without an event will be censored at the earlier of the last contact date (Last known date patient alive in “Survival Information” section) or Day 30. Subjects without any information after baseline will be considered censored at 1 day.

Table 5.2-7: Censoring and time rules

		Status	Time
Death occurred:			
	Difference between date of death and date of randomization +1 day >30 days	Censored	30 days
	Difference between date of death and date of randomization +1 day ≤30 days	Event	Calculated difference
No death occurred:			
	Difference between date of last survival status* and date of randomization +1 day >30 days	Censored	30 days
	Difference between date of last survival status* and date of randomization+1 day ≤30 days	Censored	Calculated difference

* Last survival status is the last known date patient was alive

Treatment groups will be compared using a generalized Wilcoxon test. The Kaplan-Meier estimates of the survival functions for each treatment group will be plotted and summarized.

Re-hospitalization post-discharge

Patients not discharged from the index hospitalization will not be included in the summary of number of re-hospitalizations.

The number of re-hospitalizations per patient by treatment group will be described. Treatment groups will be compared using a Wilcoxon rank-sum test.

The number of patients with re-hospitalization will be summarized. Categories of patients' number of re-hospitalizations will be 0, 1, 2, >2, and will be compared between treatment groups with a Chi-Square test. In case of cell frequencies less than 5, Fisher's Exact test will be used. Cochran-Armitage Test for trend will also be performed.

Statistical Analysis Plan

Sponsor: NOVARTIS

Protocol number: CRLX030A3301

Patients not discharged from the index hospitalization will be included in the analysis of time to first re-hospitalization.

Time to first re-hospitalization (in days) will be defined as the first re-hospitalization date (Date of admission in "Rehospitalization Information") minus the randomization date plus 1 day. Subjects still in hospital at Day 30 will be censored at Day 30, calculated as randomization date + 30 days. Subjects who die after index hospitalization discharge or when not hospitalized will be assigned the date of death as their time to re-hospitalization. Similarly, subjects who died during index hospitalization without being discharged will have their date of death as their time to re-hospitalization.

Table 5.2-8: Censoring and time rules

	Status	Time
Patient not discharged from index hospitalization at Day 30	Censored	30 days
Patient not discharged but who died during index hospitalization:		
Difference between date of death and date of randomization +1 day >30 days	Censored	30 days
Difference between date of death and date of randomization +1 day \leq 30 days	Event	Calculated difference
Patient discharged from index hospitalization and with at least one re-hospitalization:		
Difference between date of first re-hospitalization and date of randomization +1 day >30 days	Censored	30 days
Difference between date of first re-hospitalization and date of randomization +1 day \leq 30 days	Event	Calculated difference
Patient discharged from index hospitalization but without re-hospitalization:		
Difference between date of last visit* and date of randomization +1 day >30 days	Censored	30 days
Difference between date of last visit* and date of randomization +1 day \leq 30 days	Censored	Calculated difference
Patient discharged from index hospitalization but who died without re-hospitalization:		
Difference between date of death and date of randomization +1 day >30 days	Censored	30 days
Difference between date of death and date of randomization +1 day \leq 30 days	Event	Calculated difference

* Last visit includes date of last visit (if subject is alive at the study termination)

Treatment groups will be compared using a Gehan's generalized Wilcoxon test. The Kaplan-Meier estimates for each treatment group will be plotted. Descriptive statistics by treatment group will be presented.

	<h2 style="margin: 0;">Statistical Analysis Plan</h2>
	Sponsor: NOVARTIS Protocol number: CRLX030A3301

Re-hospitalisation characteristics, such as type of re-hospitalisation (urgent/emergency or elective) and reason (both primary and detailed), will be described presenting absolute frequencies and percentages calculated on the total of re-hospitalizations occurred with non-missing information. Estimated duration (days) for specific acute care units (recorded on the “Rehospitalization information” eCRF page) will be summarized by treatment group providing number of observations, mean, standard deviation, median, first and third quartiles, minimum and maximum. Absolute and relative frequencies of patients presenting at least one re-hospitalisation by type (urgent or elective) and by primary reason will be provided; percentages will be computed using the total number of patients discharged from index hospitalization as denominators.

All procedures/tests/treatments performed (recorded on the “Rehospitalization – procedures/tests/treatments performed” eCRF page) will be summarized presenting number and percentage of subjects reporting the procedure/test/treatment; the data will be summarized overall and percentages will be calculated using subjects with at least one re-hospitalization as denominators. Tabulation will follow the code list reported in the eCRF.

Resource utilization

Summary statistics on data about healthcare resource utilization collected throughout the index hospitalization, at discharge and at Day 5, and then at Day 14 post randomization, and through phone contact at Day 30 post randomization will be provided by treatment group.

Index hospitalization length of stay (days) for specific acute care units will be summarized by treatment group providing number of observations, mean, standard deviation, median, first and third quartiles, minimum and maximum. Total length of stay for each specific acute care unit will be calculated by summing the estimated duration (days) at each assessment point.

Absolute frequencies and percentages of subjects discharged and location of discharge (home / long term care facility) will be provided by treatment group.

In addition, description of emergency/urgent care > 24 hours not resulting in admission will be provided by treatment. Number of subjects with 0, 1, 2, >2 events will be summarized and compared between treatment groups with a Chi-Square test. In case of cell frequencies less than 5, Fisher's Exact test will be used. Cochran-Armitage Test for trend will also be performed.

Reason for emergency/urgent care visit > 24 hours not resulting in admission (both primary and detailed) will be described presenting absolute frequencies and percentages calculated on the total of emergency/urgent care visits with non-missing information. Absolute and relative frequencies of patients presenting at least one emergency/urgent care visit by primary reason will be provided; percentages will be computed using the total number of patients discharged from index hospitalization as denominators.

All tests performed at the emergency/urgent care visit will be summarized presenting number and percentage of subjects reporting the test; the data will be summarized overall and percentages will be calculated using subjects with at least one emergency/urgent care visit as denominators. Tabulation will follow the code list reported in the eCRF.

	<h2 style="margin: 0;">Statistical Analysis Plan</h2>
	Sponsor: NOVARTIS Protocol number: CRLX030A3301

Health-related Quality of Life

Health-related quality of life assessments, by means of the EuroQoL EQ-5D-5L questionnaire, will be used to derive pre-specified quality of life scores according to the EuroQoL EQ-5D-5L questionnaire manual.

The EQ-5D-5L consists of 5 dimensions (mobility, self-care, usual activities, pain/discomfort, anxiety/depression); each dimension has 5 levels of answer: no problems, slight problems, moderate problems, severe problems, and extreme problems. The patient is asked to indicate his/her health state for each of the 5 dimensions; the decision results in a 1-digit number expressing the level selected for that dimension. The digits for 5 dimensions can be combined in a 5-digit number describing the subject's health state. It should be noted that the numerals 1-5 have no arithmetic properties and should not be used as a cardinal score. A total of 3,125 possible health states are defined; each state is referred to in terms of a 5-digit code.

Each dimension will be summarized at baseline and at each assessment time point by treatment group providing absolute and relative frequencies of each level answer (percentages will be calculated on non-missing data for each dimension). Results will be provided also for subgroup variables such as age (i.e., <65 vs. \geq 65 years), gender and region (i.e., Eastern Europe vs. Western Europe).

EQ-5D-5L levels will be also dichotomised into 'no problems' (i.e., level 1) and 'problems' (i.e., levels 2 to 5), therefore changing the profile into frequencies of reported problems. Dichotomised variable in the two groups will be compared by means of Chi square test at each assessment time point. In case of cell frequencies less than 5, Fisher's Exact test will be used.

Each dimension will be summarized at Day 2, Day 5 and Day 14 assessment time points post randomization by treatment group, also providing absolute and relative frequencies of each level answer (percentages will be calculated on non-missing data for each dimension) by baseline level answer and by hospitalization status (hospitalized/not hospitalized) at study visit.

Summary statistics (number of observations, mean, standard deviation, median, first and third quartiles, minimum and maximum) of raw data and change (absolute and %) from baseline will be provided at each assessment time point for the subject's overall self-rated health status measure (EQ VAS values) by treatment group and by hospitalization status (hospitalized/not hospitalized) at study visit. The value of 100 is the best health the subject can imagine; 0 is the worst health the subject can imagine. Treatment groups will be compared for changes (absolute) from baseline using t-tests.

Summary statistics of raw data and change (absolute and %) from baseline will also be provided at each assessment time point for subgroup variables such as age (i.e., <65 vs. \geq 65 years), gender, region (i.e., Eastern Europe vs. Western Europe), and occurrence of at least one WHF through Day 14.

If data do not respect normality assumption, a Wilcoxon rank sum test will be applied.

	<h2 style="margin: 0;">Statistical Analysis Plan</h2>
	Sponsor: NOVARTIS Protocol number: CRLX030A3301

EQ-5D-5L health states will be converted into a single index value using UK as the reference country for all countries. Studies that derive values sets and procedure for the index computation are under development in a number of countries; the most updated SAS code from the EQ Executive Office will be applied (i.e. reference set for UK updated on January 2016 obtained from *“Devlin, N., Shah, K., Feng, Y., Mulhern, B. and van Hout, B., 2016. Valuing Health-Related Quality of Life: An EQ-5D-5L Value Set for England. OHE Research Paper 16/01. London: Office of Health Economics”*). Summary statistics will be provided for the index value at each visit by treatment group.

To compare treatment groups in quality of life change from baseline (i.e., randomization), a mixed model for repeated measures will be fitted to overall health index score absolute changes from baseline (score at time of assessment - score at baseline), and considering treatment, visit and treatment by visit as factors, and value at baseline as covariate.

If data do not respect normality assumption, a rank transformation will be applied.

The questionnaire/scale completion status will be summarised descriptively by treatment group at each visit.

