8.5 Adjudication Committee

To strengthen the efficacy findings and interpretation, a Central Event Committee will be instituted and will oversee the adjudication of in-hospital WHF events and the cause of death.

A charter of responsibilities and a specific dataset to evaluate clinical cases will be available before study initiation (Endpoint Manual).

The adjudication committee will review and adjudicate all in-hospital WHF that occur through Day 5 for endpoint determination in a blind way, as well as the causes of death events. The detailed definitions of the endpoints, required documentation, and the adjudication process will be provided to all sites in a separate Endpoint Manual.

9 Data analysis

All the data collected in this study will be listed and summarized as appropriate as described below. The data from all countries and all centers will be pooled and summarized. Continuous data will be summarized by the mean, standard deviation (SD), median, first and third quartiles, minimum and maximum. Categorical data will be presented by absolute and relative frequencies (n and %) or contingency tables.

Subjects will be included in each efficacy analysis based on available assessments, after the data handling conventions have been applied. The prevalence approach, if not differently indicated, will be applied.

Unless stated otherwise, two-sided p values <0.05 will be considered statistically significant. All statistical tables, listings and analyses will be produced using SAS® release 9.2 or later (SAS Institute, Inc, Cary, NC, USA).

More details about data analysis will be provided in the Statistical Analysis Plan.

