5.2. EFFICACY DATA

The primary analysis and the analyses of all secondary and exploratory efficacy variables will be based on the FAS. In addition to the primary analysis, the primary efficacy variable will also be analysed using the same primary analysis model on the PP set as supportive information.

Primary efficacy parameter

Worsening Heart Failure/all cause death through Day 5

The primary efficacy variable of the study is the time to in-hospital Worsening of Heart Failure (WHF) requiring rescue therapy or all cause death through Day 5 post randomization.

In-hospital worsening of heart failure (WHF) through Day 5 post randomization includes worsening signs and/or symptoms of heart failure that require an intensification of intravenous therapy for heart failure or mechanical ventilation, renal or circulatory support. Such treatment can include the institution or up-titration of IV furosemide, IV nitrates or any other IV medication for heart failure, or institution of mechanical support such as assisted (invasive or non-invasive) ventilation, ultrafiltration, hemodialysis, intra-aortic balloon pump or ventricular assist device, etc. This endpoint also includes patients who die in this 5-day period of any cause before experiencing episode(s) of WHF.

Time to in-hospital WHF/all cause death through Day 5 post randomization will be analysed using survival analysis.

The time to in-hospital WHF/all cause death will be computed as the number of hours from randomization to the earlier of the onset of in-hospital WHF or death plus 1 minute. The onset of in-hospital worsening heart failure through Day 5 will be the start date/time of event

Statistical Analysis Plan

Sponsor: NOVARTIS

Protocol number: CRLX030A3301

reported at the first assessment point at which the investigator reported worsening heart failure; if death occurred, date and time are reported in the dedicated eCRF section. Subjects without an event will be censored at the earlier of the last post-baseline assessment date or 120 hours after randomization. Subjects without any information after baseline (i.e., randomization) will be considered censored at 1 minute.

In case of missing time of in-hospital WHF or death then 00:00 will be imputed.

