Only adjudicated endpoints will be counted in the primary analysis. The “adjudicated endpoint” refers to an endpoint and date of the endpoint that has been confirmed by an independent adjudication committee who has no access to the treatment code. According to the information from the endpoint adjudication committee, the following rules will be applied to determine if an event reported in eCRF should be considered valid for the analysis or not:

Table 5.2-1: Rule for inclusion of events into the analysis

Included in the analysis	
WHF/death reported in the dedicated page of the eCRF and confirmed by adjudication committee	YES
WHF/death reported in the dedicated page of the eCRF and NOT confirmed by adjudication committee	NO

If more than one in-hospital WHF occurred, the first one will be used as the event. Censoring and time will be defined according to the following rule:

Table 5.2-2: Censoring and time rules

	Status	Time
At least one in hospital WHF and/or death occurred and:		
Difference between date and time of first occurrence of WHF/death and date and time of randomization +1 minute >120 hours	Censored	120h
Difference between date and time of first occurrence of WHF/death and date and time of randomization +1 minute \leq 120 hours	Event	Calculated difference
No in hospital WHF and death occurred and:		
Difference between date and time of last assessment* and date and time of randomization +1 minute >120 hours	Censored	120h
Difference between date and time of last assessment* and date and time of randomization +1 minute \leq 120 hours	Censored	Calculated difference

* Last assessment is the date and time of last available post-baseline physician assessment of in-hospital WHF

In case a patient is lost to follow-up, events occurring prior to the time of lost to follow-up will be counted. If no event occurred, then the patient will be censored at the time of last post-baseline in-hospital WHF assessment available.

The primary statistical hypothesis is:

	Statistical Analysis Plan
	Sponsor: NOVARTIS Protocol number: CRLX030A3301

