An additional supportive analysis of the primary efficacy variable will be performed using all WHF/all cause deaths through Day 5 post randomisation as reported by the investigators, regardless of confirmation from the endpoint adjudication committee.

The time to WHF/all cause deaths through Day 5 post randomisation will be as described for the primary analysis.

	Statistical Analysis Plan
	Sponsor: NOVARTIS
	Protocol number: CRLX030A3301

The Kaplan-Meier estimates of the survival functions for each treatment group will be plotted. Kaplan-Meier estimates at selected time points and their 95% confidence intervals will be provided.

Handling of missing values/censoring/discontinuations

In the analysis of time to in-hospital WHF/all-cause death through Day 5, patients without any event will be censored at the earlier of the last post-baseline physician assessment of in-hospital WHF or 120 hours post randomization.

Subjects without any information after baseline (i.e., randomization) will be considered censored at 1 minute.

In case of missing time of in-hospital WHF or death then 00:00 will be imputed.

Secondary efficacy parameters

The additional efficacy endpoints will be analysed in the FAS. Standard descriptive statistics will be presented for each treatment group at each time point that the endpoint was measured. Two-sided p-values <0.05 will be considered statistically significant; no adjustment for multiple comparisons will be adopted.

Time to in-hospital WHF/All cause death/readmission for heart failure through Day 14 post randomization

Time to in-hospital WHF/all cause death/readmission for heart failure through Day 14 post randomization will be analyzed using survival analysis.

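### As written, SAP 5.2 leaves a reported but unconfirmed death by Day 5 out of an all-cause-death endpoint, and its 00:00 rule for missing event times has no floor at randomization (minor)

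*SAP*

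**What the plan says.** **Death.** SAP 5.2 defines the primary endpoint as in-hospital WHF or death of any cause: "This endpoint also includes patients who die in this 5-day period of any cause before experiencing episode(s) of WHF". It then adds a filter: "Only adjudicated endpoints will be counted in the primary analysis". An adjudicated endpoint is "an endpoint and date of the endpoint that has been confirmed by an independent adjudication committee". Table 5.2-1 places WHF and death in the same row, and the answer for "WHF/death reported in the dedicated page of the eCRF and NOT confirmed by adjudication committee" is NO. Table 5.2-3 repeats this for events within Day 5 in the Day-14 endpoint, but counts WHF and deaths after Day 5 without confirmation.

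Table 5.2-2 assigns status and time. Its second half opens "No in hospital WHF and death occurred and", so it divides patients by occurrence and does not mention confirmation. The text on missing values adds that "patients without any event will be censored at the earlier of the last post-baseline physician assessment of in-hospital WHF or 120 hours post randomization".

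Other sections treat death differently:
- Protocol 9.7 and SAP 2.5 (sample size) attach the word adjudicated to WHF; death is simply all-cause.
- Protocol 8.5 has the committee review in-hospital WHF through Day 5 "as well as the causes of death events", and leaves the process elsewhere: "The detailed definitions of the endpoints, required documentation, and the adjudication process will be provided to all sites in a separate Endpoint Manual".
- SAP 4.1 counts all deaths through Day 30, adjudicated or not.

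**Missing times.** SAP 5.2 sets a missing time of WHF or death to 00:00. Time runs from randomization (SAP 5.1), plus 1 minute. Table 5.2-2 classes every difference of at most 120 h as an event at that difference. The only 1-minute rule is for censored patients with no information after baseline.

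**The concern.** Adjudication serves a purpose for WHF, which needs judgement and is reported by unblinded investigators. Whether a patient died needs little judgement, and the cause has no bearing on an all-cause endpoint. A rule that can leave out a reported death therefore does not fit the endpoint it serves, and it acts on the most objective component.

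The consequence for such a patient is also not written down. Reading Table 5.2-1 with the missing-value text, a patient with no earlier confirmed WHF would apparently be censored at the last WHF assessment, capped at 120 h. That is an inference, because Table 5.2-2 has no row for this case. Censoring shortly before a death would be informative.

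The missing-time rule can produce a negative survival time. That is not a valid value, and the SAP leaves its handling to whatever the software does.

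**Working it through.** **1. Is the plan's own figure reproducible?** The inputs behind the 3,183 patients are redacted in both documents, so only the 2:1 split can be checked: 3,183 / 3 = 1,061 on standard of care (SOC) and 2,122 on serelaxin.

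**2. Death rules side by side.**

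| Place | Is confirmation needed for a death to count? |
|---|---|
| SAP 5.2, endpoint definition | Not mentioned; any cause |
| SAP 2.5, Protocol 9.7 | No; adjudicated qualifies WHF only |
| SAP Table 5.2-1 (Day 5) | Yes |
| SAP Table 5.2-3, within Day 5 | Yes |
| SAP Table 5.2-3, after Day 5 | No |
| SAP 4.1, death through Day 30 | No |

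**3. Missing time on the randomization date.** Time = 00:00 - randomization time + 1 minute.
- Randomized 00:01: 0 minutes.
- Randomized 00:02: -1 minute.
- Randomized 18:00: -18 h + 1 min = -17 h 59 min = -17.98 h.

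Each value is at most 120 h, so Table 5.2-2 calls it an event.

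**4. Effect per record (assumed rates).** The documents give no current event rates by arm. The highest pair used is the earlier phase III trial's 12.0% vs 6.5% (Protocol 1.1): 1,061 x 0.12 + 2,122 x 0.065 = 265.3 events. The Amendment 4 rationale says events are fewer than expected, so lower pairs are also shown. Simulation: 600 trials per pair; event times truncated exponential (mean parameter 60 h, range 0-120 h); an uncounted death is censored 0-24 h before it occurred. Negative Z favours serelaxin.

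| SOC / serelaxin | Mean events | One SOC death not counted | One serelaxin death not counted | Sum: one SOC + two serelaxin |
|---|---|---|---|---|
| 4.5 / 3.25% | 117 | +0.124 | -0.073 | -0.022 |
| 6.0 / 4.3% | 154 | +0.107 | -0.064 | -0.021 |
| 7.0 / 5.1% | 182 | +0.099 | -0.058 | -0.017 |
| 9.0 / 6.8% | 240 | +0.086 | -0.050 | -0.014 |
| 12.0 / 6.5% | 265 | +0.077 | -0.053 | -0.029 |

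The last column adds single-record changes. Additivity looks adequate: three SOC deaths in the first row gave +0.375, against 3 x 0.124 = 0.372.

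For a result exactly at Z = -1.96 (one-sided p = 0.0250):
- One SOC death lost: p = 0.0301 (shift +0.08) to 0.0329 (shift +0.12).
- One serelaxin death lost: p = 0.0222 (Z = -2.01) to 0.0212 (Z = -2.03).

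**5. Effect of negative times.** For three such records, the mean absolute change in Z was 0.0022-0.0038 if kept, and the same to within 0.0001 with a floor at randomization. The Gehan test uses the order of times, and these events sort first or nearly first either way. If software dropped the three records, the change was 0.090-0.132.

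**The case against.** **Confirmation may be harmless.** The SAP defines adjudication as confirming an endpoint and its date. The endpoint is death of any cause, so a death cannot fail on cause, and confirmation would mean only that it happened and when. Protocol 8.5 does not bar the committee from checking this. In an open-label trial with a 120 h limit, a blinded check of the date is defensible. This stands as a fair reading, and on it no valid death is lost. It is not written down, however, and the manual that would settle it is not among the documents.

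**The tables can be read in order.** Table 5.2-1 decides which events are valid, and Table 5.2-2 then applies to those. This also stands. It removes the gap between rows but not the exclusion, and clearer headings would settle it.

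**The Day-5 split follows the scope of adjudication.** Only events through Day 5 go to the committee. That explains why Table 5.2-3 has two rules. It does not explain why an all-cause death needs confirmation in one period.

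**Other analyses show the deaths.** SAP 5.2 prespecifies an analysis of all investigator-reported events, all deaths enter the Day-30 analysis, and SAP 5.3 lists every death. Protocol 8.1 requires full source verification of primary data. These make an omission visible and unlikely, but they do not correct the primary test. The analysis of reported events also readmits every unconfirmed WHF, so it does not isolate deaths, and the only outputs listed for it are Kaplan-Meier curves and estimates.

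**Negative times hardly matter.** True if the records are kept. That software would drop them is an assumption, not something the documents show.

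**Conclusion.** Both rules are wrong as written, and both points are minor. Read literally, the confirmation filter can leave a reported death out of an all-cause-death endpoint. The 00:00 rule can produce a negative event time.

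A reader might infer that the plan removes genuine deaths on the ground of cause, or that the primary result is biased towards one arm. The documents support neither. The definition of adjudication allows the verified-occurrence reading, and the committee has no access to the treatment code. The documents give no share of unconfirmed deaths or missing times, so the number of affected records is unknown and may be zero. Losses in the 2:1 allocation ratio nearly cancel: about -0.01 to -0.03 in Z for one SOC and two serelaxin deaths. A single lost death would matter only in a close result, and it could move p either way. Negative times matter only if the records are dropped, at about 0.09-0.13 in Z for three records.

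All effect sizes rest on the assumed event rates and event-time distribution. The inconsistency between sections and the negative-time arithmetic do not.

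**What to change.** **Deaths.** Require committee confirmation for WHF only. Count every death with a verified date within 120 h (336 h for the Day-14 endpoint) as an event, whatever its adjudicated cause. If *confirmed* already means this for deaths, one sentence saying so is enough. Reword the headings of Tables 5.2-2 and 5.2-4 so that they refer to confirmed WHF (where confirmation applies) or death, and every patient fits a row. Align the within-Day-5 rows of Table 5.2-3.

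**Missing times.** Impute the later of 00:00 on the event date and the randomization time, so that the computed time is at least 1 minute. Apply this to the primary endpoint and to Tables 5.2-4 and 5.2-6.

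**Cost.** Two SAP sentences, reworded table headings and a few lines of derivation code before database lock. The one new risk is counting a misdated death, which the date verification guards against.
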